### 437 **2.f Early Withdrawal of Subjects**

438 If a subject decides to withdraw from all components of the research study, the

439 investigator will discontinue all of the current and scheduled research activities in the

440 study. Participants taking an intervention medication at the time of withdrawal will be

441 provided with a taper-down schedule based on maximum intervention dose achieved.

442

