### 443 **2.g** When and How to Withdraw Subjects

444 A participant can withdraw consent for the study at any time. Participants will be allowed 445 to end participation in the study at any point should they desire. If a participant must be 446 withdrawn due to a drug-related serious adverse event, then blind will be broken and, if 447 on gabapentin, drug withdrawal will be tapered or completely stopped based on the 448 clinical judgement of the PI. All participants will have an exit interview to ascertain any 449 adverse effects and discuss the reason for ending participation. The study team will 450 follow them for safety reasons up to 30 days after stopping use of the study drug.

451

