### 452 **2.h Data Collection and Follow-up for Withdrawn Subjects**

453 If a participant has ended participation, the only data that will be collected are the data
454 from the exit interview and the data collected prior to withdrawal. There will not be any
455 other follow-up or data collected from these subjects.

456

457 Data collected up to this point will not be used in the analysis, and further data will not be458 collected from these participants.

459

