### 468 **3.b Treatment Regimen**

469 During the titration period of maximum 4 weeks, participants randomized to 470 the gabapentin arm will take gradually titrated dosages of gabapentin as follows:

- 471 Week 1, 900 mg/d (300 mg TID)
- 472 Week 2, 1800 mg/d (600 mg TID)
- 473 Week 3, 2700 mg/d (900 mg TID)
- 474 Week 4, 3600 mg/d (1200 mg TID)
- 475
- 476 If intolerable effects occur, dosage will be decreased by 1 dose (300 mg) step (e.g. if
- 477 2700 mg/d is intolerable, dosage will be decreased to 2400 mg/d). Further de-escalation

478 will be determined by PI clinical judgement to prior tolerable dose. The highest tolerable

479 dose established during the Titration Period will be maintained throughout the 8-week 480 Fixed-Dose period.

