### 587 Gabapentin (300 mg pill) Titration Schedule

588

586

589 If at any point during the Titration Period, the participant wishes to discontinue 590 the medication for any reason, they will be instructed to follow the taper down schedule 591 (see below) in order to safely stop the medication. The participant will be informed that 592 any abrupt stoppage of gabapentin could cause serious adverse effects.

Participants will be contacted by telephone or video call by the Research Assistant
(RA) at the end of Titration period. The purpose of this call will be to query the
participants about adverse effects. Participants will be provided with a paper calendar
and asked to maintain diaries of olfactory and taste symptoms and adverse effects
possibly related to the intervention.

598 Participants will not complete any forms at the completion of Titration period.599 Instead, they will proceed directly to Fixed-Dose Period.

### 600 601

Fixed-Dose Period: duration 8 weeks

602During the Fixed-Dose period, participant's dose will remain at their maximum tolerated603dosage established during the Titration phase. The study drug will be distributed in eight604separate vials representing the eight weeks of the Fixed-Dose period. The RA will605contact the participants at the end of Week 4 to administer the blind assessment using606REDCap (survey titled: "Blind Assessment"). Participants will complete the following607forms after completing the Fixed-Dose Period (survey titled: "FixedDoseSurvey"):

- 608
- 609 1.) Clinical Global Impression of Severity Scale (CGI-S).

610 2.) Clinical Global Impression of Improvement Scale (CGI-I)

- 611 3.) University of Pennsylvania Smell Identification Test (UPSIT)
- 612 4.) Olfactory Dysfunction Outcomes Rating (ODOR)
- 613 5.) *NASAL-7*
- 6.) *Clinical Global Impression-Severity Scale for Parosmics (CGI-P)*
- 615 7.) Adverse Event assessment
- 616 8.) Compliance
- 617

618 *Adverse events*. Any unintentional or unfavorable clinical sign or symptom, any new

619 illness or disease or the deterioration of existing disease or illness, or any clinically

620 significant deterioration in any laboratory assessments or clinical tests while participating

621 in this study will be captured. The study coordinator will contact participants virtually to

622 answer questions and assess adverse effects after Titration period, Fixed-Dose period,

- 623 and 4 weeks after Taper.
- 624

- 625 Taper Down: maximum duration 2 weeks

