### The specific monitoring plan for this study is based on the potential risk of participation

and size and complexity of the planned investigation. Based on these considerations, this

- study will have a monitoring committee comprised of [name], [name], and
- 654 [name], the study biostatistician. All reports of a Serious Adverse Event (SAE) or

- 655 an Unexpected Adverse Event (UAE) will be investigated by the monitoring team and 656 reported to Washington University HRPO according to the reporting requirements. 657 658 Participants who experience serious adverse effects with gabapentin therapy will be 659 removed from the study. Participants with serious adverse effects will be instructed to 660 call 911, seek immediate medical care and discontinue all further gabapentin treatment. If 661 tolerated, all participants will complete the Titration period ( $\leq 4$  weeks), Fixed-Dose 662 period (8 weeks), and Taper-Down period (2 weeks) for maximum 14 weeks of active participation. In addition, there will be a 4-week, post-Taper completion follow-up for 663 664 maximum total of 18-week trial duration.
- 665 **3.a Medical Monitoring**
- 666

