### 667 i Investigator only

668 The PI and the study team will be monitoring patients for any safety concerns, such as 669 SAE or UAE, in real time for the duration of the 18-week study. In addition, participants 670 will be specifically asked about any adverse events after the Fixed-Dose period via 671 REDCap. Participants will be able to get in touch with a member of the study team 24/7via phone or pager for the duration of the 18-week clinical trial. The study biostatistician 672 673 will hold the randomization codes and remain blinded to the intervention assignment. In 674 the event of an SAE or UAE in which the blind needs to be broken, the Research 675 Pharmacist will be contacted by the PI or a member of the study team. The participant 676 will receive appropriate care and will be removed from the trial. A description of the 677 event will be included in the report of adverse events for the clinical study. 678

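### Section 2.h stops outcome collection and discards earlier data for anyone who has ended participation, which cannot be reconciled with the promised intention-to-treat analysis

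*Combined protocol and SAP*

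**What the plan says.** **Withdrawn participants.** Under E2 2.h, once a participant has ended participation, the only data are those from the exit interview and those gathered before leaving. There is to be no "other follow-up or data collected from these subjects". The section then states: "Data collected up to this point will not be used in the analysis". E2 2.g limits the exit interview to adverse effects and the reason for leaving. It also says that the team will "follow them for safety reasons up to 30 days after stopping use of the study drug".

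**Analysis.** G3 names intention-to-treat as the primary analysis, with everyone kept in the assigned group. The response rate in C3 has all participants in each group as its denominator. G4 assumes that missing data are missing at random and makes no adjustment for them.

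**Stopping drug.** E2 2.f opens: "If a subject decides to withdraw from all components of the research study, the" investigator ends all research activities. F2 begins a separate instruction: "If at any point during the Titration Period, the participant wishes to discontinue" the medication, and answers it with a taper. D3 allows step-down to no capsules at all. E3 3.b says that the highest tolerable "dose established during the Titration Period will be maintained throughout the 8-week" Fixed-Dose period.

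**Removal.** F3 3.a (Safety and Compliance Monitoring) begins: "Participants who experience serious adverse effects with gabapentin therapy will be" taken out of the study. F3 3.a (Medical Monitoring) says that, after a serious or unexpected event for which the blind has to be broken, the participant "will receive appropriate care and will be removed from the trial".

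**The concern.** An analyst who follows 2.h drops randomised participants. An analyst who follows G3 and C3 keeps them. The plan does not say which rule prevails, so the analysis set for the primary outcome is open to choice after the data are seen.

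The rule also bars ratings that could have been obtained. Surveys are remote, and a person who has stopped capsules can usually still answer them. If leaving is related to tolerability, it may differ between arms, because F2 specifies an inert placebo. The comparison of those who remain is then no longer protected by randomisation. G1 expects 33% dropout, so up to a third of those randomised could be affected, although G1 gives neither causes nor a split by arm.

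**Working it through.** **Step 1. Whom each sentence affects.** The primary CGI-I is rated once the 8-week Fixed-Dose period is over, at week 12 with a full 4-week titration. F2 has participants complete no forms at the end of titration. Taper (up to 2 weeks) and the final 4 weeks run to week 18.

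| Time of leaving | Primary CGI-I recorded? | What loses it |
|---|---|---|
| Before the FixedDoseSurvey | No | The bar on further collection in 2.h |
| During taper or the final 4 weeks | Yes | The exclusion sentence in 2.h |

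In the second row nothing is missing, so the missing-at-random assumption in G4 does not justify the exclusion. In the first row, deleting the exclusion sentence alone would not change the CGI-I result. The rating has to be collected.

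**Step 2. The plan's own precision.** Inputs from G1: 60 enrolled, 33% dropout, 40 evaluable (20 per arm), placebo response 30%, target difference 25 points, hence 55% on gabapentin.

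- Dropout: 60 × 0.67 = 40.2, about 40.
- Half-width = 1.96 × √(0.55 × 0.45/n + 0.30 × 0.70/n) = 1.96 × √(0.4575/n).
- n = 20: 1.96 × 0.1512 = 29.6 points, so 25 ± 29.6 = −4.6 to 54.6. This reproduces the −5% to 55% in G1.

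**Step 3. Precision if leavers are rated.** Same formula:

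- n = 25 (half the leavers rated): 26.5 points.
- n = 30 (every leaver rated): 24.2 points.

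**Step 4. Effect on the estimate.** Assumptions: 30 randomised per arm (60 in G1, 1:1 allocation; the 20 per group in E3 3.c matches the evaluable number); 10 leave each arm before the survey; the 20 who stay respond 55% v 30%, that is 11 v 6. Let q_g and q_p be the proportions of leavers who would respond if rated. The documents give neither.

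- Those who stay: 11/20 − 6/20 = 25.0 points.
- All randomised: (11 + 10q_g)/30 − (6 + 10q_p)/30 = 16.7 + 33.3 × (q_g − q_p) points.
- Leavers like the others (0.55 and 0.30): 16.7 + 33.3 × 0.25 = 25.0.
- All leavers at 30%: (11 + 3)/30 − (6 + 3)/30 = 46.7% − 30.0% = 16.7.
- If q_g − q_p exceeds 0.25, the all-randomised difference is above 25.0.

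The bias can therefore be nil or go either way, depending on unknown responses among leavers.

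**The case against.** **Stopping capsules does not necessarily mean leaving.** A reader might infer that the protocol makes every drug stop a study exit. The documents do not support that. The condition in 2.f is withdrawal from every component, which implies that something less is possible. D3 lets the dose fall to zero and then carries the established dose forward without mentioning withdrawal. F2 answers a wish to stop the medication with a taper only. What stands is that this person's status is not clearly defined, so staff could classify identical cases differently. The F2 flow chart could not be read and might say more.

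**Counting unrated leavers as non-responders.** One might take the C3 denominator to mean this and report a gap of 8.3 points with 10 leavers per arm (25.0 against 11/30 − 6/30 = 16.7). C3 does not state such a rule, and G4 points away from it by making no adjustment. The 16.7 in the working comes from rated leavers responding at 30% in both arms. It coincides only because the formula depends on q_g − q_p, which is zero in both cases.

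**Removal is limited.** Not every unexpected event leads to removal. The two F3 passages cover serious adverse effects, and serious or unexpected events for which the blind must be broken.

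**Loss was budgeted, and this is a pilot.** G1 enrols 60 to obtain 40 evaluable cases, so its stated precision is not undermined. But budgeting for loss does not reconcile 2.h with G3, and D3 intends the results to support a larger trial.

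**Conclusion.** The conflict between 2.h on one side and G3 and C3 on the other is in current text and needs no assumption. It should be resolved before analysis. Two separate defects produce it: a sentence that discards recorded outcomes of late leavers, and a bar on collecting outcomes from early leavers. Removal from the study after serious events adds to the second.

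The consequence is less certain. With 10 of 30 leaving each arm and 55% v 30% among those who stay, the all-randomised difference is 16.7 points if every leaver would respond at 30%, and 25.0 if leavers resemble the others. Neither case can be preferred from the documents. A reader might infer from the inert placebo that the result favours gabapentin. Differential loss is plausible, but no rate by arm is given, so that inference is not established. The gain in half-width from 29.6 towards 24.2 points reaches 24.2 only if every leaver is rated.

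**What to change.** 1. In E2 2.h, delete the sentence excluding data collected before withdrawal.
2. In E2 2.h and F2, state that stopping study drug is not a study exit. Unless consent to follow-up is withdrawn, the participant completes the FixedDoseSurvey, including CGI-I, on the planned date (week 12 if titration was not finished) and is analysed as randomised. Record the date of stopping.
3. In both F3 3.a passages, replace removal from the study or trial with removal from study drug, and flag any rating made after unblinding.

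Dosing decisions stay with the trial's clinicians.

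**Cost.** Protocol wording and a field in REDCap. The surveys are remote and already planned for everyone, and E3 3.e provides two-weekly check-ins. Some leavers will need contact beyond the 30-day safety period, and an UPSIT that they would not now receive. Some ratings will be made off drug, so the estimate describes the assigned regimen rather than 8 uninterrupted weeks of treatment. That is what an intention-to-treat analysis estimates. People who withdraw consent to follow-up will still be unrated.

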### 460 E3 Study Drug

461

### 462 **3.a Description**

463 Gabapentin is an antiepileptic medication now used as first-line therapy for diabetic 464 neuropathy and herpetic neuralgia. Gabapentin works by binding to voltage-gated 465 calcium channels (VGCCs), which play an important role in neuronal synaptic 466 transmission. More specifically, gabapentin binds to  $\alpha_2\delta$  isoforms which have been 467 associated with neuropathic pain.

### 468 **3.b Treatment Regimen**

469 During the titration period of maximum 4 weeks, participants randomized to 470 the gabapentin arm will take gradually titrated dosages of gabapentin as follows:

- 471 Week 1, 900 mg/d (300 mg TID)
- 472 Week 2, 1800 mg/d (600 mg TID)
- 473 Week 3, 2700 mg/d (900 mg TID)
- 474 Week 4, 3600 mg/d (1200 mg TID)
- 475
- 476 If intolerable effects occur, dosage will be decreased by 1 dose (300 mg) step (e.g. if
- 477 2700 mg/d is intolerable, dosage will be decreased to 2400 mg/d). Further de-escalation

478 will be determined by PI clinical judgement to prior tolerable dose. The highest tolerable

479 dose established during the Titration Period will be maintained throughout the 8-week 480 Fixed-Dose period.

#### 481 3.c Method for Assigning Subjects to Treatment Groups

482 The participants will be divided using permuted block randomization in a 1:1 allocation

- 483 between two arms: the oral gabapentin group and the oral lactose placebo group with 20
- 484 persons in each group.

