### 413 2.d Randomization Method and Blinding

414 Participants who remain eligible at the end of the screening period will be randomized in 415 a double-blind fashion, according to a computer-generated random code, to receive either 416 placebo or gabapentin. [name] will provide the randomization table to the BJH 417 Research Pharmacist, who will prepare both gabapentin and placebo for the entire study. 418 The research assistants will collect the gabapentin and placebo in a blinded fashion from 419 the research pharmacist for distribution to the participants via FedEx.

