### 794 G1 Sample Size Determination and Power

795 To date there have been no studies investigating efficacy of gabapentin in COVID-19 796 related olfactory dysfunction. Due to the lack of preliminary data and effect size, 797 estimates of the sample size for this study will be determined based on feasibility. For 798 this pilot study, we plan to enroll 60 subjects. The sample size of 60 subjects is feasible 799 given the incidence of COVID-19 cases in Missouri and considering a conservative 800 estimate of a 10% rate of permanent olfactory dysfunction among those (~50%) who 801 experience olfactory dysfunction as one of the presenting symptoms. Using a 33% drop 802 out rate, we estimate that the sample size of 60 subjects randomized in a balanced way 803 between the two treatment groups will provide us with 40 evaluable cases. A previous 804 study exploring a different treatment for COVID-19 related anosmia in our lab showed 805 that 30% of the participants randomized to placebo reported improvement at the end of 806 the trial as compared to baseline. We aim to observe a 25% difference in the response 807 rate between gabapentin and placebo groups. Assuming that this will be the response rate 808 in the placebo group of our trial, the sample size of 20 subjects per group will provide us 809 with a 95% Confidence Interval -5% to 55% around the desired proportion difference of 810 25% between gabapentin and placebo groups.

811

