### 814 G3 Statistical Methods

815 An intention-to-treat analysis will be used for the primary analysis of the data. All

816 participants will be examined in the groups to which they were initially assigned.

817 Standard descriptive statistics will be used to assess the demographics, clinical

818 characteristics, and olfactory test results of the study population. The difference in rate of

responders after Fixed-Dose period will estimate the effect size of the primary outcome

820 measure, and the 95% CI around that point estimate will measure precision. In each

group, the frequency and relative frequency of the participants' response to the global

rating of smell change will be reported for each Likert category. Fisher's exact test will

be used for comparing the responders' rates between the 2 groups. Histograms and

- 824 Shapiro-Wilks test will be used to test the normal distribution assumption of the
- 825 continuously measured UPSIT scores and the differences pre-post treatment in each of
- the groups. Independent samples t-test or its nonparametric equivalent Mann-Whitney U
- test will be used to compare the change in UPSIT scores between the two groups. Mixed
- 828 effects model will be used to test whether the change in UPSIT score from baseline to
- end of treatment is significantly different between 2 groups. Subjects will be treated asrandom factors, and group and time will be used as fixed factors in the model. Interaction
- of group by time will be explored. Effect sizes with 95% CIs will be reported for each
- analysis. All statistical analyses will be conducted in SPSS 28 (IBM Corp., Armonk,
- 833

NY).

834

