## 835 G4 Missing Outcome Data

All attempts will be made using Good Clinical Practice and through the reduction of the complexity and number of assessments to minimize the occurrence of missing outcome data. It will be assumed that all missing data will be at random. As this is a small pilot study, no computational techniques will be employed to adjust analyses for missing data.

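### Section 3.c assigns 20 persons per group (40 in all) while G1 randomises 60 to leave 20 evaluable per group; the number randomised must be one figure

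*Combined protocol and SAP*

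**What the plan says.** Section E3 3.c, on how subjects are assigned to treatment, specifies permuted-block randomisation in a 1:1 ratio "between two arms: the oral gabapentin group and the oral lactose placebo group with 20" persons in each group. Two groups of 20 make 40 assigned; the total is not printed there.

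Section G1 plans to enrol 60. It then says, on a 33% dropout rate, "we estimate that the sample size of 60 subjects randomized in a balanced way" "between the two treatment groups will provide us with 40 evaluable cases". Balanced randomisation of 60 is 30 per group, a figure G1 does not print. G1 goes on to state that 20 subjects per group will give an estimate "with a 95% Confidence Interval -5% to 55% around the desired proportion difference of" 25%, taking a 30% placebo response from an earlier study of a different treatment in the same laboratory.

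Sections E2 2.d and E3 3.h describe the randomisation table and its handover to the research pharmacist, "who will prepare both gabapentin and placebo for the entire study", but give no count. In the readable text, 3.c and G1 are the only places that state how many are to be randomised.

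**The concern.** Both sections speak of randomisation, and their totals are 40 and 60. Nothing in 3.c marks its 20 as evaluable or completing participants, and dropout is not known when people are assigned. The 20 per group in G1 is what remains after dropout.

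G1 sets the size on feasibility and gives no power target, so the 95% interval is the only quantitative support for the sample size. As G1 reasons it, that interval depends on randomising 60. The number randomised also fixes the length of the allocation list, the amount of drug to prepare, and the denominator of any analysis by assigned group. A list or supply built from 3.c would be one third short of G1's plan. The documents do not show which number was used.

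**Working it through.** **Inputs.** From 3.c: 20 persons per group, 1:1. From G1: 60 enrolled and randomised, dropout 33%, 40 evaluable, 20 per group for the interval, placebo response 30%, target difference 25 points (hence 55% on gabapentin), stated interval -5% to 55%.

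**1. G1's evaluable number.** Evaluable = randomised × (1 − dropout) = 60 × 0.67 = 40.2, which matches G1's 40, or 20 per group. In reverse, 40 / 0.67 = 59.7, rounded up to 60.

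**2. G1's interval.** Unpooled Wald 95% interval: d ± 1.96 × √[p₁(1−p₁)/n₁ + p₂(1−p₂)/n₂], with d = 0.55 − 0.30 = 0.25. The variance terms are 0.55 × 0.45 = 0.2475 and 0.30 × 0.70 = 0.2100, which sum to 0.4575. At 20 per group, √(0.4575/20) = 0.1512 and 1.96 × 0.1512 = 0.296. The interval is -4.6% to 54.6%, which rounds to G1's -5% to 55%. G1 is therefore consistent with itself at 60 randomised and 20 evaluable per group.

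**3. The two totals.** 3.c: 2 × 20 = 40. G1: 60. The difference is 20, and 20/60 is one third.

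**4. If 3.c is followed and dropouts leave the analysis.** 40 × 0.67 = 26.8, about 27 evaluable in total. Holding the rates at 30% and 55%:

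| Evaluable (gabapentin / placebo) | Half-width (points) | 95% interval |
|---|---|---|
| 13 / 13 | 36.8 | -11.8% to 61.8% |
| 13 / 14 | 36.2 | -11.2% to 61.2% |
| 14 / 13 | 36.1 | -11.1% to 61.1% |
| 14 / 14 | 35.4 | -10.4% to 60.4% |

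With 27 evaluable the interval is about -11% to 61%. The half-width is about 36 points, against about 30 in G1.

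**5. If everyone assigned is counted.** With the same rates, 20 per group (3.c) gives -4.6% to 54.6% as in step 2. For 30 per group (G1), 1.96 × √(0.4575/30) = 0.242, giving +0.8% to 49.2%.

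**6. Which of steps 4 and 5 the plan follows.** The documents point both ways. G1 reasons from evaluable cases. Section E2 2.h says of withdrawn participants "Data collected up to this point will not be used in the analysis", and G4 says "no computational techniques will be employed to adjust analyses for missing data"; these take dropouts out. G3 says "An intention-to-treat analysis will be used for the primary analysis of the data", and the primary outcome in C3 divides responders by the participants in each group; these keep everyone in.

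**The case against.** The strongest reply is that a reader with both sections can recover the intention. G1 is the sample-size section, it gives the whole chain from 60 enrolled to 20 evaluable per group, and its arithmetic is sound. On this view the 20 in 3.c is simply that evaluable number carried over, and no test, estimand or interval in G1 needs to change. The likely origin can be granted. It explains the discrepancy without removing it: 3.c is the section that governs assignment, and it gives a number that G1's reasoning does not support.

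The second reply is that the loss of precision needs three things together: 3.c is followed, dropout reaches 33%, and dropouts leave the analysis. Under G3's intention-to-treat rule, 40 randomised would still give about -5% to 55%. This stands. The wider interval is a conditional illustration, and the conflict over who is analysed is a separate matter. It is also fair that the pilot has no power target and that its planned interval already includes zero, so no claim about power is made here.

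A third reply is that the flow chart and some front matter are not readable in the copy reviewed and might carry a count. The statement that only 3.c and G1 give the number is therefore limited to the readable text. A count elsewhere would still leave these two sections in disagreement. Nor is the absence of a pharmacy count evidence that the list or supply is short; that needs only to be confirmed.

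Reading G1's 60 as enrolled and 3.c's 40 as randomised does not help. G1 itself says the 60 are randomised and calls the 33% a dropout rate, and F1 places the eligibility smell test before consent.

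**Conclusion.** The contradiction holds and must be fixed. The number to randomise is 40 in 3.c and 60 in G1, a difference of 20, and nothing in the readable text reconciles them. G1's figures reproduce at 60 randomised and 40 evaluable, so 3.c is the outlier; G1's calculation is not at fault.

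If 3.c were followed, with 33% dropout and dropouts excluded, about 27 would be evaluable and the interval would be about -11% to 61% instead of -5% to 55%. If all assigned were counted, the intervals would be about -5% to 55% with 40 randomised and +1% to 49% with 60. All of these assume response rates of 30% and 55% and G1's Wald-type interval. The inconsistency itself depends on none of these assumptions.

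**What to change.** In 3.c, replace the group size with wording such as: *30 persons randomised to each group (60 in total, about 20 evaluable per group after 33% dropout)*. Confirm that the permuted-block list and the pharmacy's supply cover 60.

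If 40 randomised is the real target, leave 3.c as it is and restate G1: enrolment 40, about 27 evaluable after 33% dropout, and an interval of about -11% to 61% on the evaluable-case reasoning that G1 uses.

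The first option costs one line of protocol text and one check with the biostatistician and research pharmacist. G1's enrolment target is already 60, so it adds no participants to that plan.
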